15.1.2 SECONDARY ENDPOINTS

- At end of study review all alerts from Path Active and responses to the alerts. Was ulceration prevented? Were there any conflicting outcomes from device use?

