4.0 STUDY FLOW CHART

5.0 INTRODUCTION

5.1 BACKGROUND

More than 4.9M people have been diagnosed with diabetes (DM) in the UK, and up to 25% (1.2M) will develop a Diabetic Foot Ulcer (DFU) in their lifetimes. 15-20% of DFUs lead to amputations which are followed by significantly increased mortality. The cost to taxpayers is enormous (Kerr 2019), consuming 1% of NHS budget annually.

The current method of providing periodic foot checks is inadequate, with the chance of recurrence of an ulcer being 40% in the first year, rising to almost 100% over 10 years (Armstrong 2017). Individuals at high risk of DFU go to clinic to have their feet checked at least once a month. This can be highly disruptive to their everyday lives. Furthermore, there is considerable environmental cost of patient travel and if a DFU occurs single-use consumables for treatment such as dressings, bandages, scalpels, blood tests, cultures for microbiology , etc.

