6.2 SECONDARY AIMS

To model the carbon dioxide reduction that may occur if ulceration and the need for ulcer treatment is prevented, in differing UK geographies.

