7.0 TRIAL DESIGN

7.1 METHOD

Study setting

Participants who have been assessed as having a 'high risk' of foot ulceration will be recruited from Community Foot Protection Teams in 4 sites across the UK. Participants will be recruited to the study to a maximum total of 120 (30 at each site) who have completed the study. The number of recruits required is based on a power calculation for the study at the 95% confidence interval.

The study is anticipated to run for 12 months.

Procedure

Potential participants will be approached to participate during routine review by the Community Foot Protection Teams and consented by them for the study. All participants will be screened at pre-assessment by the Community Foot Protection Teams.

Following completion of informed consent the participant will have;

- Medical History
- Arterial Doppler scan

- Test for Neuropathy
- Eligibility confirmation
- EuroQoL Assessment (EQ-5D-5L)
- Patient Questionnaire
- Randomised to 'Path Active Group' or 'Control Group' using computer randomisation.

If the participant is randomised to use the device in the 'Path Active Group';

- Participant Training in device and mobile app use (Appendix 1).

If there is an alert from Path Active app the participant will be asked to reduce walking and rest their feet. If the alert continues and activates the clinical dashboard, patients will be contacted to attend clinic for review.

If the participant is not randomised to use the device in the 'Control Group', they will continue with their regular podiatry clinical reviews with the Community Foot Protection Team who will provide their standard of care.

Day 84 (week 12). At the end of study;

- EuroQoL Assessment (EQ-5D-5L)
- Patient Questionnaire

If the participant is randomised to use the device;

- Device retained by clinical research team.

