15.0 ENDPOINT DESIGN

15.1 ENDPOINTS

15.1.1 PRIMARY ENDPOINTS

- Day 84 all participants will be asked to complete a health-related quality of life questionnaire and a questionnaire regarding patient experience and, for the Path Active Group, use of the device and suggested improvements with the device and associated 'app'.
- To model any reduction in carbon footprint due to ulcer prevention.

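### Section 15.1.2 asks whether ulcers were prevented by reviewing alerts in the device arm alone, which cannot tell an averted ulcer from a false alert

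*Protocol*

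**What the plan says.** Section 15.1.2 gives one secondary endpoint: "At end of study review all alerts from Path Active and responses to the alerts. Was ulceration prevented". It is the only listed endpoint that asks whether ulcers were prevented. Its analysis, in Section 15.2.2, also uses alerts only, to estimate sensitivity and specificity.

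Section 7.1 describes what an alert does: "If there is an alert from Path Active app the participant will be asked to reduce walking and rest their feet". A continuing alert that reaches the clinical dashboard leads to a clinic review. Control participants have no device, hence no alerts; they continue with usual podiatry review.

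Two other places bear on the point. Section 15.1.1 lists as a primary endpoint "To model any reduction in carbon footprint due to ulcer prevention", without naming the source of the prevention figure. Sections 6.0, 6.1 and 15.2.1 promise a comparison with routine podiatry review, but no listed endpoint is ulcer incidence by arm.

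**The concern.** Prevention is a contrast between what happened and what would have happened without the device. The record of a device user shows only the former. The randomised control arm supplies the latter, but an endpoint built on alerts leaves that arm out.

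The possible error runs in the device's favour. Crediting intact feet after an alert makes a device that alerts more often look more preventive, whether or not it prevents anything. At stake is the trial's answer to its main clinical question and, if the same figure were carried into the carbon model, that result too.

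**Working it through.** The documents state no number of prevented ulcers and no alert rate, so there is no plan figure to reproduce on this point.

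**Inputs**
- Annual risk 40%, from Section 5.1: "with the chance of recurrence of an ulcer being 40% in the first year". This is a recurrence rate. The listed eligibility criteria require high-risk stratification, not a previous ulcer, so it is probably high for this population.
- Follow-up of 84 days, from Section 7.1.
- 120 completers in two arms, from Section 7.1. The allocation ratio is not stated; 1:1, or 60 per arm, is assumed.
- Constant hazard, assumed.

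**Step 1: what the alert record can show.** For a device user who has an alert and then rests:

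| Without the device | Observed | True meaning |
|---|---|---|
| would have ulcerated | no ulcer | ulcer averted |
| would not have ulcerated | no ulcer | false alert |
| would have ulcerated | ulcer | not averted |

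The first two rows look identical in the data. No review of alerts and responses separates them.

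**Step 2: how common the second row is likely to be.**
- 84-day risk = 1 − (1 − 0.40)^(84/365) = 1 − 0.889 = 0.111.
- Share ulcer-free without the device = 88.9%, or 60 × 0.889 = 53.3 of 60.
- Expected ulcers without the device = 60 × 0.111 = 6.7 per arm.

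With other annual risks, all assumed:

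| Annual risk | 84-day risk | Expected ulcers per 60 |
|---|---|---|
| 5% | 1.2% | 0.7 |
| 20% | 5.0% | 3.0 |
| 25% | 6.4% | 3.8 |
| 60% | 19.0% | 11.4 |

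These are expected numbers, so a realised count can be higher. They set the scale of what the device could prevent on average.

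**Step 3: how many could be wrongly credited.** This needs an alert rate and a crediting rule, and the protocol gives neither. Suppose that every alerted user who stays intact is credited, alerts are unrelated to risk and the device has no effect. The credited number is then (alerted users) × 0.889:
- 10 alerted: 8.9
- 20 alerted: 17.8
- 40 alerted: 35.6

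The true number in each case is 0. These figures show direction and sensitivity only; they do not predict this trial.

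**Step 4: precision of the randomised contrast.** Take 11.1% in Control and a halving to 5.5% with the device, 60 per arm, two-sided 5%.
- Difference = 0.0555, or 60 × 0.0555 = 3.3 ulcers.
- Standard error = √[(0.111 × 0.889 + 0.0555 × 0.9445)/60] = 0.050.
- 95% CI half-width = 1.96 × 0.050 = 0.098, or about 5.9 ulcers per 60.
- Power is about 19%; 80% power would need about 389 per arm.

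**The case against.** The strongest reply is that Section 15.1.2 asks an open question and sets no counting rule. It does not say that every alerted, ulcer-free participant is a prevented ulcer, and Section 15.2.2 plans a specificity estimate, which presupposes that some alerts are false. This stands, and it is why the Step 3 figures remain conditional. It does not rescue the endpoint: however the review is conducted, its source cannot separate the two rows in Step 1.

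A reader might infer that most feet that would never have ulcerated will be counted as prevented. The documents do not support that. Only alerted users could be credited, and no alert rate is given. In the 20-alert illustration, 17.8 of 53.3 is one third.

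A reader might also infer that the carbon saving will be inflated. The protocol does not say that the alert review feeds the carbon model. The aim in Section 6.2 is conditional ("To model the carbon dioxide reduction that may occur if ulceration and the need for ulcer treatment is prevented, in differing UK geographies"), and the between-arm comparison in Section 15.2.1 could supply the input. What stands is that the source is unstated, and that Section 15.1.2 is the only listed endpoint asking about prevention.

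Finally, a statistical analysis plan might settle how the question is judged. But the protocol itself ties the question to alerts, and a plan that followed this wording would inherit the problem.

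**Conclusion.** The point holds in this form: the prevention question is tied to evidence from one arm that cannot answer it, although a randomised comparator exists, and the ambiguity favours the device. It should be corrected.

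The supported size is the background: about 89% ulcer-free at 84 days without the device and about 6.7 expected ulcers per 60. This rests on applying the 40% recurrence figure to all participants, constant hazard and 1:1 allocation. A lower true risk would leave fewer ulcers to prevent and more intact feet open to misreading. The number falsely credited cannot be derived from the documents.

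**What to change.** - **Section 15.1.2:** keep the review as a description of alerts, responses and conflicting outcomes, and remove the prevention question from it. Answer that question by the difference, Control minus Path Active as randomised, in the proportion of participants with a new ulcer by Day 84, with its 95% CI. State that the difference may be zero or negative.
- **Section 15.1.1:** state that any trial-based prevention input to the carbon model is this difference with both CI limits, not a tally of alerts without an ulcer. Scenario values from outside the trial can still be used if labelled as such.

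**Cost.** The wording change is short, but it is not the whole cost. The schedule in Section 10.2 lists no foot assessment at week 12, only adverse event review, the questionnaire and EQ-5D-5L. Ulcer status must therefore be recorded at that existing visit, in the same way in both arms. Research question 1 in Section 6.0 already needs this, and no extra visits or participants follow from it. The other cost is a less certain headline: under the Step 4 assumptions the interval would run from about 2.6 ulcers caused (3.3 − 5.9) to 9.2 prevented (3.3 + 5.9) per 60. An alert tally would hide that uncertainty, not reduce it.

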15.2 ANALYSIS PLANS

15.2.1 PRIMARY ENDPOINT ANALYSIS

Day 84; Data will be analysed to determine the effectiveness of 'Path Active' compared with standard podiatry review.

Questionnaires will be reviewed for QoL outcomes and patient experience.

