6.0 RESEARCH QUESTIONS

- Is Path Active as effective as regular routine podiatry review in foot ulcer prevention?
- Does using Path Active improve participant QoL?
- Are there any suggestions from participants to improve the device/app?
- Will preventing foot ulceration reduce NHSE carbon footprint?

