17.1 DEFINITION OF THE END OF TRIAL

The last patient completing day 84 of the trial.

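### 120 participants followed for 84 days cannot settle whether Path Active prevents ulcers as well as podiatry, so the Day 84 effectiveness claim should be narrowed

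*Protocol*

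**What the plan says.** The first research question in section 6.0 of the protocol is "Is Path Active as effective as regular routine podiatry review in foot ulcer prevention". Section 6.1 makes effectiveness against routine podiatry review the primary objective.

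Section 15.2.1, the primary endpoint analysis, says "Day 84; Data will be analysed to determine the effectiveness of" Path Active against standard podiatry review. A separate sentence there covers the questionnaires. No ulcer measure is named. The primary endpoints in 15.1.1 are the Day 84 questionnaires and carbon modelling; ulceration appears in 15.1.2, inside the review of device alerts.

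On size, section 7.1 states "Participants will be recruited to the study to a maximum total of 120 (30 at each site) who have completed the study", and adds "The number of recruits required is based on a power calculation for the study at the 95% confidence interval". The reference list cites an online calculator for binary-outcome superiority trials. No event rate, effect, margin or power is given.

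On time, section 17.1 defines the end of the trial as "The last patient completing day 84 of the trial". The only ulcer risk with a period attached and below a lifetime scale is in section 5.1: "the chance of recurrence of an ulcer being 40% in the first year, rising to almost 100% over 10 years".

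**The concern.** The background describes ulcer risk over one to ten years, whereas each participant is observed for 12 weeks. Read together, sections 6.0, 6.1, 7.1 and 15.2.1 tell the reader that the trial will establish whether the device matches podiatry in preventing ulcers, and that its size was calculated. If only a handful of ulcers can occur, neither answer is safe. A moderately protective device would probably show no significant difference. A null result could be taken as showing that the device is as good as podiatry while remaining compatible with a considerably higher ulcer risk, in a population chosen for being at high risk.

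**Working it through.** **Inputs from the protocol.** Annual recurrence 40% (5.1); 84 days of follow-up (7.1, 17.1); 120 completers (7.1).

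**Assumptions, not in the protocol.** Constant hazard; equal allocation, so 60 per arm; two-sided 5% significance; 80% as the power benchmark; every participant carries the cited recurrence rate. Annual rates of 20% and 60% are shown as a range.

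**The plan's own figure.** 120 cannot be reproduced, because none of its inputs are stated.

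**Step 1: risk over 84 days.** Risk = 1 − (1 − annual risk)^(84/365).
- 40% a year: 1 − 0.6^(84/365) = 11.1%; 60 × 0.1109 = 6.7 control ulcers.
- 20% a year: 5.0%, or 3.0 control ulcers.
- 60% a year: 19.0%, or 11.4 control ulcers.
- A simple linear share of 40% gives 0.40 × 84/365 = 9.2%.

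**Step 2: power with 60 per arm.** Normal approximation: Φ(|p1 − p2| / √{[p1(1 − p1) + p2(1 − p2)]/60} − 1.96). Fisher's exact power is by full enumeration.

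| 84-day control risk | True effect | Fisher exact | Normal approx. |
|---|---|---|---|
| 11.1% | halving | 10% | 20% |
| 19.0% | halving | 23% | 32% |
| 11.1% | complete prevention | 67% | 78% |
| 19.0% | complete prevention | 98% | 96% |
| 11.1% | doubling | 28% | 38% |

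**Step 3: number needed for 80% power to detect a halving from 11.1%.** n per arm = (1.96 + 0.8416)² × [p1(1 − p1) + p2(1 − p2)] / (p1 − p2)² = 385.4, so 386 per arm against the 60 available.

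**Step 4: precision if the true risks are equal at 11.1%.** Half-width = 1.96 × √(2 × 0.1109 × 0.8891/60) = 0.112, or ±11.2 points. A doubling is a difference of +11.1 points, which lies inside that interval.

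**Step 5: the question asked as non-inferiority.** With equal true risks of 11.1% and one-sided 2.5%, the smallest margin reaching 80% power is (1.96 + 0.8416) × √(2 × 0.1109 × 0.8891/60) = 16.1 points. A 10-point margin needs 155 per arm, and a 5-point margin 620.

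**Step 6: is the horizon alone responsible?** With a full year (40% vs 20%) and the same 60 per arm, power for a halving is about 67% (normal approximation, pooled variance). A 10-point non-inferiority margin would then need 377 per arm. Longer follow-up helps the superiority comparison but does not rescue it at 120, and it makes a test on a fixed absolute margin harder.

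**The case against.** The strongest reply is that section 15.2.1 analyses primary endpoints that are questionnaires and carbon modelling, for which 12 weeks can be adequate, and that it nowhere mentions ulcers. This stands as far as it goes: the ulcer reading comes from 6.0 and 6.1, not from 15.2.1 itself. But those sections state what effectiveness against podiatry means in this trial, and 15.2.1 treats the questionnaires in a different sentence. The promise therefore reaches further than the questionnaires.

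Several stronger readings are tempting and not supported:
- *That no effect size could reach 80% power.* At exactly 40% a year complete prevention falls just short, but by the normal approximation it reaches 80% at about 41.4% a year, and by Fisher's test at about 45%. The statement also ignores large harmful effects.
- *That 84 days alone is the fault.* Step 6 shows that size and horizon act jointly.
- *That 120 was derived from a one-year rate.* Many pairs of rates give 60 per arm, and the protocol states none.
- *That the carbon model fails with the ulcer comparison.* Section 6.2 describes what may follow if ulcers are prevented. That can be modelled conditionally, without the trial's own effect estimate.
- *That the sponsor will declare equal effectiveness from a null result.* The protocol does not say so, and a statistical analysis plan that is not at hand may set the rule. The risk arises because the wording leaves that reading open.

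**Conclusion.** The concern holds in a limited form. Sections 6.0, 6.1 and 15.2.1 together promise more about ulcer prevention than 120 participants over 84 days can deliver. At the protocol's own rate, power for a halving is 10% to 20%, and the interval around no difference is as wide as the control risk itself. Low power for a halving persists across 84-day risks from 5.0% to 19.0%. The figures rest on constant hazard, 60 per arm and the recurrence rate applying to everyone. If participants without a previous ulcer have a lower rate, fewer events will occur. Nothing here shows that 120 is wrong for the questionnaire endpoints. This should be fixed, but it does not invalidate the trial as a 12-week study of quality of life and experience.

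**What to change.** Keep 84 days and 120 participants, and change what may be concluded:
- **15.2.1:** limit the Day 84 effectiveness analysis to the comparison of quality of life and patient experience. Describe any between-arm ulcer comparison as a preliminary estimate with its 95% confidence interval. State that a non-significant ulcer difference will not be read as showing the device to be as effective as podiatry.
- **3.0, 6.0 and 6.1:** align the question and objective with this.
- **7.1:** state the ulcer precision available over 84 days, about ±11 points at an 11% risk with 60 per arm, in place of wording that implies a powered ulcer comparison.
- **15.1.2:** list new ulceration in both arms as a secondary endpoint and record it for every participant at the existing Day 84 visit. The schedule in 10.2 marks no foot assessment at that visit, so the estimate otherwise has no planned source.

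A record search after Day 84 is not recommended as a substitute. Section 16.0 seeks consent for record access in the context of monitoring, audit and inspection and does not mention outcome follow-up. That time would also fall after the device has been returned.

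The cost is a less favourable stated ambition, edits to the sections named, and one extra item on the Day 84 form.

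### No single between-arm endpoint decides the trial: 15.2.1 promises a verdict on effectiveness without naming the variable, and ulcer prevention, the stated question, is not in the primary tier

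*Protocol*

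**What the plan says.** Five places in the protocol bear on which result decides the trial.

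- **6.0 Research Questions** opens with "Is Path Active as effective as regular routine podiatry review in foot ulcer prevention". Quality of life is a separate question in the same list. Section 6.1 makes effectiveness against routine podiatry review the primary aim.
- **15.1.1 Primary Endpoints** says that at Day 84 "all participants will be asked to complete a health-related quality of life questionnaire and a questionnaire regarding patient experience". Device-use items are added for the Path Active Group, and a second bullet lists a carbon-footprint model.
- **15.1.2 Secondary Endpoints** raises ulcer prevention as a question within the end-of-study review of Path Active alerts.
- **15.2.1 Primary Endpoint Analysis** has two sentences. The first is "Data will be analysed to determine the effectiveness of 'Path Active' compared with standard podiatry review". The second is "Questionnaires will be reviewed for QoL outcomes and patient experience".
- **7.1 Method** says "The number of recruits required is based on a power calculation for the study at the 95% confidence interval", without giving the outcome, rates, effect or power. The reference list in 25.0 contains an online power calculator for a binary-outcome superiority trial.

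**The concern.** A protocol should let a reader say, before any data exist, which comparison settles the main question. Here 'effectiveness' has three candidate meanings: ulceration (from 6.0), health-related quality of life, and patient experience (both from 15.1.1). Nothing in the protocol chooses among them.

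The candidates can disagree. Path Active participants wear sensor insoles and use an app, while controls continue their usual reviews, so participants know their arm. A better experience score among device users is plausible even with no difference in EQ-5D-5L or ulceration. Under the present wording that score sits in the primary tier, and 15.2.1 promises a conclusion on effectiveness compared with podiatry. A reader could take the result as an answer to the ulcer question when it is not.

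**Working it through.** **1. Do the sections agree on the deciding endpoint?**

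| Section | What it points to | Between-arm? | Tier |
|---|---|---|---|
| 6.0, first question | Ulcer prevention | Yes | Main question |
| 6.1 | Effectiveness in people at high ulcer risk | Yes | Primary aim |
| 15.1.1, first bullet | Quality of life; patient experience | Possible: both arms answer | Primary |
| 15.1.1, second bullet | Carbon model | Not a test between arms | Primary |
| 15.1.2 | Ulceration, within alert review | No: alerts arise only in the device arm | Secondary |
| 15.2.1, first sentence | Effectiveness, variable unnamed | Yes | Primary analysis |
| 25.0 | Binary outcome, superiority | Yes | Sample-size source |

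The outcome in 6.0 is missing from 15.1.1, the outcomes in 15.1.1 are not tied to effectiveness in 15.2.1, and the binary outcome implied by 25.0 is not listed as primary.

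**2. Does the sample size reveal the endpoint?**

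The only figure is "Participants will be recruited to the study to a maximum total of 120 (30 at each site) who have completed the study". Allocation is given only as "Randomised to 'Path Active Group' or 'Control Group' using computer randomisation", so I assume 1:1, which is 60 per arm. I also assume 80% power and two-sided 5%. The unpooled formula is n per arm = (1.96 + 0.8416)² × [p1(1 − p1) + p2(1 − p2)] / (p1 − p2)², where (1.96 + 0.8416)² = 7.849.

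- 20% v 4%: 7.849 × 0.1984 / 0.0256 = 60.8, so 61 per arm, 122 in total
- 30% v 10%: 7.849 × 0.3000 / 0.0400 = 58.9, so 59 per arm, 118 in total
- 40% v 17.5%: 7.849 × 0.3844 / 0.0506 = 59.6, so 60 per arm, 120 in total

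Very different assumptions give about 120. The number can be neither reproduced nor traced to an endpoint.

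**3. Illustration of what the open choice could cost**

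Three assumptions, none of them stated in the protocol: every contrast is tested two-sided at 5%, any one significant result suffices, and there is no true effect. Let k be the number of contrasts, ρ their common correlation and c = 1.96.

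- Independent contrasts: 1 − 0.95^k. For k = 2 this is 1 − 0.9025 = 9.75%. For k = 3 it is 1 − 0.8574 = 14.26%.
- Correlated contrasts: 1 − ∫ φ(u) [Φ((c − √ρ u)/√(1 − ρ)) − Φ((−c − √ρ u)/√(1 − ρ))]^k du.

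| Contrasts | ρ = 0 | ρ = 0.5 | ρ = 0.8 |
|---|---|---|---|
| 2 (quality of life, experience) | 9.8% | 9.1% | 7.8% |
| 3 (adding ulceration) | 14.3% | 12.5% | 9.8% |

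Counting only results that favour the device, against a nominal 2.5%, the figures at ρ = 0.5 are 4.5% for two contrasts and 6.3% for three. With independence they are 1 − 0.975² = 4.9% and 1 − 0.975³ = 7.3%.

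**The case against.** **The protocol sets no error rate to inflate.** This stands. A reader might infer that the plan runs at two to three times a 5% false-positive rate. The documents do not support that: the questionnaires are only to be reviewed, no test or threshold is given for any endpoint, and no rule says that one success is enough. The 95% level in 7.1 describes the sample-size calculation. Rules for ordering tests or splitting alpha are commonly left to an SAP, which is not shown, so their absence is not held against the protocol.

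**The number of contrasts is debatable.** This also stands. The second sentence of 15.2.1 can be read as saying how effectiveness will be judged, which leaves two contrasts. Ulceration is secondary under 15.1.2. If the first question in 6.0 is read as non-inferiority or equivalence, a test against no difference is not the relevant error for ulceration, and the three-contrast row does not apply.

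**The choice of endpoint could be left to the SAP.** This does not stand. An SAP details how a named primary endpoint is analysed. Which outcome decides the trial belongs in the protocol, and this protocol addresses it in 15.1.1 and 15.2.1 in ways that match neither each other nor 6.0.

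**Conclusion.** The point holds as a conflict within the protocol. Effectiveness is asked about in terms of ulcer prevention, is promised a primary analysis with no variable, and has a primary tier made up of questionnaires and a carbon model. The consequence is that a favourable questionnaire result could be presented as effectiveness against podiatry. This conclusion rests on the text alone and needs none of the error-rate figures.

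Those figures show only what the wording leaves room for: about 8% to 10% for two contrasts and 10% to 14% for three, over correlations from 0.8 to 0, under the assumptions stated in the working. They are not operating characteristics of the plan.

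**What to change.** - In 15.1.1, name one between-arm primary endpoint. In 15.2.1, analyse that same endpoint as the sole basis for the effectiveness conclusion. Sections 6.0 and 6.1 and the binary calculator point to new ulceration by Day 84, Path Active versus Control.
- Move EQ-5D-5L and patient experience (only items asked of both arms) to secondary, reported as estimates with 95% confidence intervals.
- State that a questionnaire result is reported as a quality-of-life or experience result, not as effectiveness in ulcer prevention.
- If the sponsor prefers EQ-5D-5L as primary, restate the aim and the basis for 120 to match, and keep ulceration as a between-arm secondary outcome.

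**Cost.** Most of this is wording. A favourable experience score can no longer stand alone as a primary success. If ulceration is primary, foot status must be recorded in both arms at the existing Day 84 visit, because the schedule in 10.2 lists no foot assessment there.

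The basis for 120 must also be shown, and it may not be comfortable. As an assumption, take the 40% first-year recurrence in 5.1 at a constant hazard: 1 − 0.6^(84/365) = 11.1% by Day 84. With 60 per arm, power to detect a halving of that would be about 19%. The 40% is a recurrence figure and may not fit this population, but the sponsor should settle this when choosing the endpoint.
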